9.2 Statistical and Analytical Plan

The statistical evaluation will be performed by using validated software. All data will be listed and trial summary tables will be provided. Descriptive summary statistics will be presented by group (Verum, Placebo). Standard statistical tests will be applied. A detailed plan for statistical analysis will be amended.

9.3 Demographics and Baseline Medical Characteristics

Summary statistics will be presented. Frequency tables for qualitative data will be provided. The two groups will be compared for balance in age by means of an unpaired t-test.

9.4 Definition of Study Populations for Analysis

All patients who received at least one dose of study treatment will be included in the analysis of safety.

All patients who complete the study, will be included in the analysis of immune response and efficacy. The immune results of patients who drop out before completion of the study will be analyzed in a descriptive manner. If the study should be prematurely stopped after an interim analysis (see section 9.9), the study population for clinical efficacy will be defined as all patients who completed Visit 5 after 12 Months of treatment.

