5.3.7 Early Discontinuation Visit

If the patient is prematurely discontinued from further study participation he/she will be invited to attend an early discontinuation visit. If the reason for discontinuation was an adverse event that is still present by the time of the early discontinuation visit, the adverse event will be followed up until it is resolved or stabilized.

The following procedures will be performed:

Questioning for Adverse events (see section 8.17)

Concomitant medication including insulin dose (see section 8.3)

Body weight (see section 8.4)

Vital signs (see section 8.5)

Physical examination (see section 8.6)

12-lead ECG (see section 8.7)

Safety laboratory (see section 8.8)

HCG (in women only) (see section 8.10)

HbA1c (see section 8.11)

Collection of all used, unused and partly used study medication (see section 7.3)

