6.5 Withdrawal Criteria

During the study, each subject may withdraw from further participation at any time and without giving reasons. However, adequate efforts should be made to determine the reasons for discontinuing. If a patient is lost to follow-up, adequate effort should be made to determine the whereabouts and medical status of that patient, and to recover the study medication.

Patients may be discontinued early for any of the following reasons:

- An adverse event too severe to allow continuation
- Gross patient non-compliance (e.g. if compliance of drug intake is less than 80% on two consecutive visits)
- A significant protocol violation as determined by the Study Committee
- Elevation of ALT or AST of more than 3 times the upper limit of normal
- Elevation of CPK more than 10 times the upper limit of normal, or presumed or assured diagnosis of a rhabdomyolysis
- Elevation of serum-creatinine more than 2 mg/dL
- Pregnancy or nursing occurring during the trial
- Intake of a HMG-CoA reductase inhibitor (other than the study medication) during the course of the study

If a patient is withdrawn from the study the patient should be invited to attend an Early Discontinuation Visit, the reasons for removal from the study and the date of last use of study medication should be recorded.

Patients discontinuing because of an adverse event must continue to maintain contact until the event resolves or is stable, and the information must be documented by the investigator.

Patients who did not receive any medication because of withdrawal prior to the administration of the first dose will not be assigned a patient number, and data obtained up to that point will not be entered in the study database.

Patients withdrawn from the study during the first nine months after the first intake of study drug will be replaced.

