7.6 Treatment Compliance

The investigator or designated study personnel will maintain a log of all study drug dispensed and returned. Drug supplies for each subject will be inventoried and accounted for throughout the trial.

Compliance will be determined by a capsule count at each study visit. If compliance is < 80 % at two consecutive visits the subject must be withdrawn.

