9.5 Handling of Missing and Incomplete Data

Missing or incomplete data will be reported as deviations from the protocol.

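### The efficacy analysis is restricted to patients who complete 18 months, and no C-peptide is measured after withdrawal, so randomisation does not protect the primary comparison

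*Protocol*

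**What the plan says.** Section 9.4 defines the efficacy population: "All patients who complete the study, will be included in the analysis of immune response and efficacy". The only provision there for dropouts concerns immune data: "The immune results of patients who drop out before completion of the study will be analyzed in a descriptive manner". Section 9.8 refers back to 9.4 for who enters the efficacy evaluation. Section 5.1 sets an 18-month treatment phase, and the Synopsis sets the primary endpoint, C-peptide area under the curve, at both 12 and 18 months.

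Section 6.5 lists reasons for which patients may be discontinued. They include severe adverse events, rises in ALT/AST, CPK or creatinine, and taking another statin. Low compliance is also on that permissive list, whereas Section 7.6 makes it mandatory: "If compliance is < 80 % at two consecutive visits the subject must be withdrawn". On numbers, Section 6.5 says "Patients withdrawn from the study during the first nine months after the first intake of study drug will be replaced", and Section 6.2 counts its target of 160 in completers.

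After withdrawal, Section 5.3.7 says "he/she will be invited to attend an early discontinuation visit". That visit covers HbA1c, insulin dose and safety, but neither a mixed meal test nor C-peptide. Section 8.16 schedules the meal test at Visits 1, 4 and 5 only. On missing data, Section 9.5 says only "Missing or incomplete data will be reported as deviations from the protocol".

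If the trial stops at the interim, Section 9.4 changes the set: "the study population for clinical efficacy will be defined as all patients who completed Visit 5 after 12 Months of treatment". The flow chart in Section 5.2 puts Visit 4 at 12 months and Visit 5 at 18 months.

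**The concern.** Randomisation makes the arms comparable at entry. Selecting on completion keeps that comparability only if the reasons for leaving are unrelated to arm or unrelated to C-peptide, and the protocol gives no ground for assuming either. Muscle symptoms, CPK and liver enzyme rises could be commoner on atorvastatin, and starting an outside statin could be commoner on placebo. If leavers have lower or higher C-peptide than stayers, and the arms lose different fractions, the completer means differ even when the drug does nothing. Replacing early withdrawals restores the head count but not the comparability.

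The loss is partly irreversible. A later statistical plan can redefine the analysis set, but it cannot recover meal tests that were never done. For patients who leave between months 12 and 18 the 12-month test does exist, yet it would only be listed (Section 9.2) and not used in the final primary analysis.

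**Working it through.** **Plan's own figure.** Section 9.1 gives mean 0.37, SD 0.053 nmol/l, a 20% difference and 80 per group. The target difference is 0.20 × 0.37 = 0.074. With 80 per group, z = 0.074 / (0.053 × √(2/80)) = 8.83, so the statement that this would be significant at p < 0.01 is literally true. It contains no dropout rate and no allowance for selective loss, so it cannot bound the bias.

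**Model for the bias (assumptions, not protocol figures).** 100 are randomised per arm and the drug has no effect. In each arm the fraction f with the lowest values of a latent variable leaves. That variable has correlation ρ with C-peptide.

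- Completer mean shift in SD units: ρλ(f), with λ(f) = φ(z_f)/(1 − f), where z_f is the f-quantile of the standard normal.
- λ(0.25) = 0.424, λ(0.20) = 0.350, λ(0.15) = 0.274, λ(0.10) = 0.195.
- Bias = ρ[λ(f_A) − λ(f_P)].
- Completer variance: v = 1 − ρ²(λ² − z_f λ).
- SE = √(v_A/n_A + v_P/n_P), with n the completers per arm.
- Rejection rate = P(|Z + bias/SE| > 1.96).

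Worked case, 25% v 10%, ρ = 0.5:

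- Bias = 0.5 × (0.424 − 0.195) = 0.114 SD.
- v_A = 1 − 0.25 × 0.465 = 0.884 and v_P = 1 − 0.25 × 0.288 = 0.928.
- SE = √(0.884/75 + 0.928/90) = 0.149, so the shift is 0.77.
- Rejection = P(Z > 1.19) + P(Z < −2.73) = 0.117 + 0.003 = 12%.

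| Dropout (active v placebo) | ρ = 0.2 | ρ = 0.3 | ρ = 0.5 |
|---|---|---|---|
| 25% v 10% | 6.0% | 7.3% | 12.0% |
| 20% v 10% | 5.5% | 6.1% | 8.2% |
| 15% v 10% | 5.1% | 5.3% | 5.9% |

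Simulation of the same scenarios agrees to within half a percentage point. The rejection rates do not depend on the C-peptide SD.

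**In nmol/l at the Section 9.1 SD, 25% v 10%.** For ρ = 0.2, 0.0457 × 0.053 = 0.0024, which is 3% of 0.074. For ρ = 0.5, 0.1144 × 0.053 = 0.0061, which is 8%. A larger true SD scales these up in proportion.

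**Patients outside the set.** At 25% v 10%, 25 + 10 = 35 of 200 randomised patients do not enter the efficacy analysis.

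**12-month results excluded.** The 160 are completers, so the number with a 12-month test is 160/(1 − d), where d is the fraction leaving between months 12 and 18. For d = 10% that is 178, so 18 results are excluded. For d = 5% about 8 are excluded, and for d = 15% about 28.

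**The case against.** *The protocol limits differential dropout.* Side effects can lead to dose reduction instead of withdrawal (Sections 5.1 and 7). Investigators are blinded to lipids from Visit 1 to 5 (Section 8.9), and high LDL is excluded at screening (Section 6.4), so outside statin use may be rare. Most Section 6.5 reasons are permissive, and nothing in the protocol ties them to C-peptide. All this stands as a reason to expect a modest bias. It does not restore a randomised comparison, and no second efficacy set would show whether the bias was small.

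*Analysis sets belong in the statistical plan.* The model and the missing-data method do, and they are not criticised here. The completer rule and the assessment schedule, however, are fixed in the protocol.

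*Completers only is an inference.* Section 9.4 says who is included, not that others are barred. But it gives dropouts only descriptive treatment of immune results and writes a separate rule for early stopping, which makes completion the normal condition.

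A reader might go further on four points, which the documents do not support:

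- That withdrawn patients are not followed at all. HbA1c, insulin dose and safety are collected once, and adverse events are followed until resolved or stable. C-peptide is what is missing.
- That 12-month data in general are discarded. Only those of patients who leave between months 12 and 18 are affected, in the final analysis, and they are still listed.
- That the bias could reach a third of the target difference. This needs leavers to differ from completers by something like 0.18 nmol/l, which is 3.4 times the stated SD. With SD 0.053 the largest possible gap is 0.053/√(d(1 − d)), or 0.122 at 25% dropout and 0.177 at 10%.
- That the early-stop rule would clearly admit the 12-month patient whom the final analysis excludes. Section 9.4 says Visit 5, which is month 18, so the text contradicts itself and settles nothing.

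Section 6.5 also says of patients withdrawn before the first dose that "data obtained up to that point will not be entered in the study database". This is minor: under double-blind supply, not starting is unlikely to depend on arm.

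**Conclusion.** The point holds. The protocol makes completion of 18 months the condition for entering the efficacy analysis, ties completion to post-randomisation events that may differ by arm, and obtains no C-peptide after withdrawal. The primary comparison is therefore not protected by randomisation, and the bias could run in either direction.

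On the assumptions above, the Type I error is appreciably inflated only when dropout is clearly unequal and fairly strongly related to outcome: about 12% at 25% v 10% with correlation 0.5, and close to nominal at 15% v 10%. At the stated SD the bias is small in nmol/l against the target. The case for change rests on the lost protection and on measurements that cannot be recovered later, not on a demonstrated large bias.

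**What to change.** 1. In Section 9.4, define the primary efficacy set as all randomised patients (at minimum all who took a dose), analysed as randomised and using every 12- and 18-month meal test obtained. Keep completers as a sensitivity set.
2. In Sections 5.3.7 and 6.5, separate stopping study drug from leaving the study, and invite patients off drug who still consent to the Visit 4 and Visit 5 meal tests.
3. State that a replacement adds a patient and does not remove the replaced one from the analysis.
4. Reconcile Section 6.5 (optional) with Section 7.6 (mandatory) on withdrawal for low compliance, and Section 9.4 with the Section 5.2 flow chart on which visit is at 12 months.

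The cost is protocol wording plus a modest number of additional meal tests. These are extra because early withdrawals are replaced and the target counts completers. The estimated effect may be somewhat diluted by patients off drug, and the completer sensitivity analysis can show by how much the two results differ.

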5.3.3 Visit 2

Visit 2 should be performed 3 months (± 2 weeks) after Visit 1.

The following procedures will be performed:

Questioning for Adverse events (see section 8.17)

Concomitant medication including insulin dose (see section 8.3)

Body weight and BMI (see section 8.4)

Vital signs (see section 8.5)

Safety laboratory (see section 8.8)

Serum Lipids (see section 8.9)

HCG (in women only) (see section 8.10)

Plasma CRP (see section 8.13)

Serum cytokines and chemokines (see section 8.14)

Transcriptional analysis (in a subset of 50 patients) (see section 8.15)

Collection of used, unused and partly used study medication and dispensing of study medication (see section 7.3)

5.3.4 Visit 3

Visit 3 should be performed 6 months (± 10 days) after Visit 1.

The following procedures will be performed:

Questioning for Adverse events (see section 8.17)

Concomitant medication including insulin dose (see section 8.3)

Body weight and BMI (see section 8.4)

Vital signs (see section 8.5)

Safety laboratory (see section 8.8)

Serum Lipids (see section 8.9)

HCG (in women only) (see section 8.10)

Beta-cell autoantibodies (see section 8.12)

Collection of used, unused and partly used study medication and dispensing of study medication (see section 7.3)

HbA1c (see section 8.11)

5.3.5 Visit 4

Visit 4 should be performed 12 months (± 2 weeks) after Visit 1.

The following procedures will be performed:

Questioning for Adverse events (see section 8.17)

Concomitant medication including insulin dose (see section 8.3)

Body weight and BMI (see section 8.4)

Vital signs (see section 8.5)

Safety laboratory (see section 8.8)

Serum Lipids (see section 8.9)

HCG (in women only) (see section 8.10)

HbA1c and fasting C-peptide (see section 8.11)

Beta-cell autoantibodies (see section 8.12)

Plasma CRP (see section 8.13)

Serum cytokines and chemokines (see section 8.14)

Two-hour mixed-meal tolerance test (see section 8.16)

Collection of used, unused and partly used study medication and dispensing of study medication (see section 7.3)

5.3.6 Visit 5

Visit 5 should be performed 18 months (± 2 weeks) after Visit 1.

The following procedures will be performed:

Questioning for Adverse events (see section 8.17)

Concomitant medication including insulin dose (see section 8.3)

Body weight and BMI (see section 8.4)

Vital signs (see section 8.5)

DIATOR

Protocol Version 2.3 07/01/2004

Physical examination (see section 8.6)

12-lead ECG (see section 8.7)

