8.15 Transcriptional Analysis

At Visits 1 and 2, Serum and Plasma in a subset of 50 patients will be sampled for analyses of expression of immune mediators on transcriptional level. A laboratory manual of the procedures and details of the tests will be provided prior to the start of the study.

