9.7 Evaluation of Immune Response

Patients will be included in the evaluation of immune response as outlined in section 9.4.

If appropriate, the results may be stratified for age, status of autoimmune antibodies and C-peptide levels at the entry into the study.

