9.9 Interim Analyses

Informal interim safety analyses will be performed at 6-monthly intervals during safety discussions between the Study Committee and the independent external Safety Review Board. Decisions will be made on the discretion of the investigators and the

Safety Review Board. Any changes to the study as a result of the data review will be made as amendments to the protocol.

In addition an interim analysis for clinical efficacy and immunology parameters will be performed after 40 percent of both treatment groups have completed Visit 4 (12 months of treatment). For this analysis the statistical methods described above will be applied.

At this interim analysis the determination of sample size may be adjusted based on the clinical efficacy data so far obtained. If a clinically relevant and statistically significant difference for the primary efficacy endpoint can be assessed at this interim analysis, the study can be prematurely stopped by the discretion of the Study Committee and the Safety Review Board.

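### After an early stop, section 9.4 redefines the population for clinical efficacy only, so the final between-arm immune comparison stays limited to 18-month completers

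*Protocol*

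**What the plan says.** Section 9.4 of the protocol sets one population for two analyses: "All patients who complete the study, will be included in the analysis of immune response and efficacy". The treatment phase is 18 months (5.1), and the last scheduled visit is Visit 5 (5.3.6): "Visit 5 should be performed 18 months (± 2 weeks) after Visit 1".

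For patients who leave before that, 9.4 adds: "The immune results of patients who drop out before completion of the study will be analyzed in a descriptive manner".

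If the study is stopped after the interim analysis, 9.4 replaces the population, but names one analysis only: "the study population for clinical efficacy will be defined as all patients who completed Visit 5 after 12 Months of treatment". Section 9.7 contains no rule of its own: "Patients will be included in the evaluation of immune response as outlined in section 9.4".

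The interim analysis itself has the wider scope (9.9): "an interim analysis for clinical efficacy and immunology parameters will be performed after 40 percent of both treatment groups have completed Visit 4".

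Immune sampling is spread over the study. Immune mediators are taken at Visits 1, 2, 4 and 5 (8.14). Autoantibodies are taken at screening and Visits 3, 4 and 5 (8.12). Transcriptional work ends at month 3 (8.15): "At Visits 1 and 2, Serum and Plasma in a subset of 50 patients will be sampled".

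**The concern.** The protocol treats clinical efficacy and immune response as separate analyses: they have their own sections (9.8 and 9.7), and 9.9 lists both. A clause that changes the set for clinical efficacy therefore does not, on its wording, change it for immune response. After an early stop the immune set would still be the study completers.

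On that path, patients with complete samples at months 3, 6 or 12 would be left out of the final comparison for objective 5 because they had not reached a visit that those samples do not depend on. Recruitment date would be the main reason for their exclusion, so the chief cost is precision.

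The same criterion also acts in a trial that runs to full length. A patient in the transcriptional subset has given everything that analysis needs by month 3, yet is compared only if he or she completes month 18. Selection on later completion uses information arising after randomisation. Some withdrawal reasons in 6.5, such as liver enzyme or CPK elevation, could be related to treatment, so completers need not be comparable between arms.

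**Working it through.** Section 9.4 states no figure to reproduce. The check has two parts: what the wording implies, and how many patients it could affect.

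**Wording**

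- Default set, immune and efficacy: study completers (9.4), with an 18-month treatment phase (5.1).
- Early-stop set, clinical efficacy: redefined in 9.4.
- Early-stop set, immune response: not mentioned in 9.4; 9.7 points back to 9.4. The default remains.
- Visit named in the early-stop clause: Visit 5 and 12 months together. But 5.3.5 says "Visit 4 should be performed 12 months (± 2 weeks) after Visit 1", and Visit 5 is month 18. The clause contradicts itself on which visit defines even the efficacy set.

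**Size**

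Inputs from the protocol: at most 160 completers (5.1, 6.2); interim when 40% of both groups have completed Visit 4 (9.9); Visits 2, 4 and 5 at months 3, 12 and 18 (5.2).

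Assumptions, because the protocol gives neither an accrual period nor a stopping delay: uniform accrual of 160 patients over A months, no dropout, and a stop at the interim data cut.

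- Time of the cut: T = 12 + 0.4A.
- Patients who have reached month m: 160 × (T − m)/A, kept between 0 and 160.
- Month 12: 160 × 0.4 = 64.
- Month 18: 160 × (0.4 − 6/A), which is zero for A up to 15.
- Share of month-12 patients without Visit 5: (6/A)/0.4 = 15/A, for A of 15 or more.
- Standard-error ratio, completers against month-12 patients: √(64/month-18 number).

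| A (months) | T | Month 3 | Month 12 | Month 18 | Month-12 patients without Visit 5 | Month-3 patients without Visit 5 | SE ratio |
|---|---|---|---|---|---|---|---|
| 18 | 19.2 | 144 | 64 | 11 | 83% | 93% | 2.4 |
| 24 | 21.6 | 124 | 64 | 24 | 62.5% | 81% | 1.6 |
| 30 | 24.0 | 112 | 64 | 32 | 50% | 71% | 1.4 |
| 36 | 26.4 | 104 | 64 | 37 | 42% | 64% | 1.3 |
| 48 | 31.2 | 94 | 64 | 44 | 31% | 53% | 1.2 |

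If patients continue for d months between the cut and the stop, T becomes 12 + 0.4A + d and the loss shrinks:

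- d = 3: 37 of 91 month-12 patients have Visit 5 at A = 18 (59% without), and 44 of 84 at A = 24 (48% without).
- d = 6: 64 of 117 at A = 18 (45% without), and 64 of 104 at A = 24 (38% without).

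**The case against.** **The data are not discarded.** This stands. Section 9.4 keeps the immune results of patients who drop out, for description. What is at risk is the between-arm comparison. The fallback is itself uncertain, because 9.4 does not say whether a patient whose follow-up ends with the study counts as a drop-out.

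**The interim analysis already covers immunology.** This also stands. An efficacy stop follows the interim analysis, which is triggered by Visit 4 completion and includes immune parameters. A reader might infer from 9.4 that, with fast accrual, the immune comparison would be made in nobody. The protocol does not support that for the trial as a whole, since 9.9 provides an immune analysis before the stop. But 9.9 names no separate population and does not define the immune set for the final report.

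**Completing the study might mean something shorter once the study is shortened.** Possible, but 9.4 does not say so. It also saw a need to redefine the efficacy set for this case, which suggests the default was not meant to adjust by itself.

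**Efficacy and immune results might not rest on different patients.** A reader might infer that they would. That holds only if 12 months governs the early-stop clause. If Visit 5 governs, both sets are 18-month completers and the contrast disappears. The restriction on the immune set remains under either reading.

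**This could be left to the analysis plan.** Section 9.2 does defer details. The population, however, is already fixed in 9.4 and adopted by 9.7, so the issue is a stated rule, not an omission.

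**Conclusion.** The point holds as a minor one. Section 9.4, read literally, limits the final immune comparison after an early stop to patients who reached Visit 5, and ties the month-3 transcriptional comparison to 18-month completion even in a full-length trial.

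A reader might go further and conclude that most patients with immune data are lost. The protocol does not establish that. Among month-12 patients the share without Visit 5 exceeds half only if accrual takes less than 30 months with no stopping delay, and delay lowers it. Among month-3 patients it is above half throughout the 18-to-48-month range without delay, but that too rests on uniform accrual and no dropout.

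The consequence is confined to objective 5, which is neither the primary nor the secondary efficacy endpoint, and its larger part arises only on the early-stop path.

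**What to change.** In 9.4:

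1. Extend the early-stop clause so that it covers *clinical efficacy and immune response*.
2. In the same sentence, reconcile Visit 5 with 12 months.
3. Compare each immune parameter in all randomised patients who have a baseline value (the screening value for autoantibodies) and a value at the visit concerned, whether or not month 18 was reached. For the transcriptional subset that visit is month 3.
4. Keep the completer analysis as a sensitivity analysis.

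The first two changes close the early-stop gap. The third also removes the unneeded completion criterion in a full-length trial. No new samples or visits are required. The cost is a short rewording, numbers analysed that differ by visit, and a few more tables.
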